5.4.1.2.3 Robustness with respect to use of prohibited medication and procedures

These sensitivity analyses will assess the robustness of the results of the main analysis with respect to the assumption that use of prohibited medication and procedures, cf. CTP Panel 7, has no influence on the endpoint of interest among subjects not discontinuing IMP. This will be done by excluding data collected after use of prohibited medication and procedures. Missing data resulting from such exclusions will be imputed in separate sensitivity analyses based on each of the following imputation algorithms:

- Non-responder imputation.
- ‘Delta-adjusted’ pattern-mixture model.

For subjects using prohibited medication and procedures or experiencing intercurrent events to be addressed by ‘composite’ or ‘hypothetical’ strategies cf. [Panel 11](#), the data observed after the occurrence of such events will be excluded from the imputation models.

Following these exclusions, multiple imputation of missing scores will be done just as in the main analysis (including the use of the same seeds) for missing data, which

- did not arise after use of prohibited medication and procedures, or
- did arise after use of prohibited medication and procedures that happened after the occurrence of intercurrent events to be addressed by ‘composite’ or ‘hypothetical’ strategies (i.e. the value of the estimand’s variable will in such a case be determined by the strategy for addressing the intercurrent event).

THIS DOCUMENT CONTAINS CONFIDENTIAL INFORMATION AND MUST NOT BE COPIED OR MADE AVAILABLE TO ANY THIRD PARTY WITHOUT THE PRIOR WRITTEN CONSENT OF THE LEO PHARMA GROUP

For the sensitivity analysis based on non-responder imputation, all binary response values corresponding to missing data arising after use of prohibited medication and procedures that did not happen after the occurrence of intercurrent events to be addressed by ‘composite’ or ‘hypothetical’ strategies, will be imputed as non-responses.

For the sensitivity analysis based on ‘delta-adjusted’ pattern-mixture models, imputed scores will, as described in section 5.4.1.2.1, be adjusted by a specified margin Δ (Panel 13) for missing scores arising after use of prohibited medication and procedures that did not happen after the occurrence of intercurrent events to be addressed by ‘composite’ or ‘hypothetical’ strategies.

If use of prohibited medication and procedures occurs on the same date as an intercurrent event or an endpoint assessment, the use of prohibited medication and procedures will be assumed to have occurred last.

5.4.2 Primary estimand for time-to-event endpoints

For the primary estimands associated with time-to-event endpoints, Panel 14 provides an overview of those strategies that are specified in Panel 2 for addressing each of the intercurrent events described in section 5.3.

Panel 14. Intercurrent event strategies for primary estimands associated with time-to-event endpoints

Type of endpoint	Estimand	Strategy for addressing IE		
		Permanent discontinuation of IMP independent of pandemic restrictions	Permanent discontinuation of IMP due to pandemic restrictions	Unblinding of subject
Time-to-event	Primary	‘While on treatment’: The IE is accounted for as a competing risk in a competing risks model	‘Hypothetical’: Occurrences of the IE will lead to right censoring, assumed to be non-informative, in a competing risks model	‘Treatment-policy’: Occurrences of the IE will be ignored

Abbreviations: IE = intercurrent event; IMP = investigational medicinal product.

[figure not shown]

THIS DOCUMENT CONTAINS CONFIDENTIAL INFORMATION AND MUST NOT BE COPIED OR MADE AVAILABLE TO ANY THIRD PARTY WITHOUT THE PRIOR WRITTEN CONSENT OF THE LEO PHARMA GROUP

The primary estimand for time-to-event endpoints can be seen to assess the treatment response prior to permanent discontinuation of IMP regardless of subjects becoming unblinded, if permanent discontinuation of IMP due to pandemic restrictions would not occur.

Panel 15 describes the competing risks model mentioned in **Panel 14** as part of the strategy for addressing the two intercurrent events related to permanent discontinuation of IMP. For subjects permanently discontinuing IMP due to pandemic restrictions, the time to event will be right censored at the time of discontinuation. This is thought of as a ‘hypothetical’ strategy, the envisaged scenario being that permanent discontinuation of IMP due to pandemic restrictions would not occur and that among those at risk of an event at time t , the event hazards of those who experienced permanent discontinuation of IMP due to pandemic restrictions at time t are similar to the hazards of those who did not experience it.

Panel 15. Competing risks model describing the primary estimand for time-to-event endpoints

Abbreviations: IMP = investigational medicinal product.

5.4.2.1 Main analysis

The null hypothesis,

$$H_0: \lambda_{\text{broda}}(t) = \lambda_{\text{gus}}(t), \text{ for all } t \in (0, 28),$$

where $\lambda(t)$ denotes the sub-distribution hazard rate associated with the time-to-event endpoint at time t , measured in weeks, will be tested against the alternative,

THIS DOCUMENT CONTAINS CONFIDENTIAL INFORMATION AND MUST NOT BE COPIED OR MADE AVAILABLE TO ANY THIRD PARTY WITHOUT THE PRIOR WRITTEN CONSENT OF THE LEO PHARMA GROUP

$$H_1: \lambda_{\text{broda}}(t) \neq \lambda_{\text{gus}}(t), \text{ for some } t \in (0, 28),$$

based on Gray's test, stratified by baseline body weight (≤ 100 kg, > 100 kg).

To quantify the magnitude of the potential treatment effect, the estimated cumulative incidence functions for the competing risks model displayed in [Panel 15](#) will be presented for the groups defined by treatment arm and baseline body weight (≤ 100 kg, > 100 kg), based on the Aalen-Johansen estimator, along with pointwise 95% confidence bands. Differences between treatment groups in the estimated cumulative incidence functions for the model will also be presented for each baseline body weight stratum (≤ 100 kg, > 100 kg), along with corresponding 95% CIs. Additionally, the estimated sub-distributional hazard ratios comparing treatment arms and corresponding 95% CIs for the 2 competing risks based on fitting Fine and Gray models, stratified by baseline body weight (≤ 100 kg, > 100 kg) and adjusted for the baseline PASI score will be presented.

In addition to permanent discontinuation of IMP due to pandemic restrictions – which will be considered a potential right-censoring event as part of the estimand strategy – the main analysis will consider the following as potential right-censoring events.

- **Completion of trial (administrative censoring).** This potential right-censoring event will be taken to have occurred if 'Did the subject complete the trial?' is answered 'Yes' on the 'End of trial' eCRF form. The timing of the event will be taken as the reported 'Date of last contact'.
- **Withdrawal from trial.** This potential right-censoring event will be taken to have occurred if 'Did the subject complete the trial?' is answered 'No' on the 'End of trial' eCRF form. The timing of the event will be taken as the reported 'Date of last contact'.

We refer to these as 'potential' right-censoring events since they will only lead to right-censoring if, by the time of their occurrence, the subject is still at risk for the two events shown in [Panel 15](#). If a potential right-censoring event happens on the same date as one of the events illustrated on [Panel 15](#), the latter will be assumed to have happened first.

It is important to note that for endpoints that are only assessed at trial visits, e.g. PASI score, the above specified analysis implicitly ignores the intermittent inspection process. The time to achieving the endpoint, e.g. PASI 100 response, is imputed based on the trial visit where the

THIS DOCUMENT CONTAINS CONFIDENTIAL INFORMATION AND MUST NOT BE COPIED OR MADE AVAILABLE TO ANY THIRD PARTY WITHOUT THE PRIOR WRITTEN CONSENT OF THE LEO PHARMA GROUP

[figure not shown]
response is first observed. Also, unless subjects who achieve the time-to-event endpoint maintain it until the time of their next visit, they will not be observed to have experienced the event.

5.4.2.2 Sensitivity analyses

5.4.2.2.1 Robustness with respect to intermittent follow-up

For a given subject in the main analysis, the time to response while remaining on treatment is imputed using the scheduled timing of the visit where the desired response is first observed. In order to assess the robustness of the results of the main analysis with respect to this imputation strategy, the probability of achieving a response prior to discontinuation of IMP independent of pandemic restrictions will be estimated based on the multi-state model illustrated in [Panel 16](#).

Panel 16. Multi-state model for the sensitivity analysis accounting for the intermittent nature of the observation process

Abbreviations: IMP = investigational medicinal product.

For this analysis, we formulate the likelihood function for an intermittently observed continuous-time Markovian 3-state process $\{Z(t) | 0 \leq t\}$ in terms of its transition probabilities, as in [\(3\)](#). Given a subject-specific vector of time-fixed covariates \mathbf{x} and states j, k of the 3-state process, the transition probability

$$p_{jk}(s, t | \mathbf{x}) = \text{Prob}\{Z(t) = k | Z(s) = j, \mathbf{x}\}$$

is the probability that a subject in state j at time s will be in state k at time t for $0 \leq s \leq t$.

Letting n denote one of the N randomised subjects in the trial we let

THIS DOCUMENT CONTAINS CONFIDENTIAL INFORMATION AND MUST NOT BE COPIED OR MADE AVAILABLE TO ANY THIRD PARTY WITHOUT THE PRIOR WRITTEN CONSENT OF THE LEO PHARMA GROUP

$$0 = v_{n,0} < v_{n,1} < \dots < v_{n,M_n} \leq 28$$

denote the (potentially subject-specific) inspection times, measured in weeks after randomization, and we let

$$z_{n,0}, z_{n,1}, \dots, z_{n,M_n}$$

denote the states observed for the subject at these times. A subject could be observed to be a non-responder (or responder) and permanently discontinue IMP independently of pandemic restrictions at one and the same visit, say at the Week 20 visit. Such a situation will be interpreted as observing the subject to be in the ‘Non-responder (Randomised)’ (or ‘Responder’) state at the inspection time 20 weeks and observing the subject to be in the ‘Permanent discontinuation of IMP independent of pandemic restrictions’ state at the inspection time 20.1 weeks.

Conditional on the initial distribution of subjects amongst states and the distribution of covariates, the likelihood function can then be written as the product of independent contributions L_n from each of the N randomized subjects of the trial:

$$L = \prod_{n=1}^N L_n = \prod_{n=1}^N \prod_{m=1}^{M_n} p_{z_{n,m-1} z_{n,m}}(v_{n,m-1}, v_{n,m} | \mathbf{x}_n).$$

Under certain regularity conditions, we can consider the transition intensities

$$q_{jk}(t | \mathbf{x}) = \lim_{\Delta t \rightarrow 0} \frac{p_{jk}(t, t + \Delta t | \mathbf{x})}{\Delta t} \quad \text{for } 0 \leq t \text{ and states } j, k \text{ with } j \neq k$$

and

$$q_{jj}(t | \mathbf{x}) = - \sum_{k \neq j} q_{jk}(t | \mathbf{x}) \quad \text{for } 0 \leq t \text{ and states } j.$$

Conversely, the transition probability matrix (p_{jk}) can, again under certain regularity conditions, be retrieved from a given transition intensity matrix (q_{jk}) using the Kolmogorov differential equations.

THIS DOCUMENT CONTAINS CONFIDENTIAL INFORMATION AND MUST NOT BE COPIED OR MADE AVAILABLE TO ANY THIRD PARTY WITHOUT THE PRIOR WRITTEN CONSENT OF THE LEO PHARMA GROUP

The sensitivity analysis will estimate state occupation probabilities for the model displayed in [Panel 16](#) for the groups defined by treatment arm and randomisation strata. This will be done using the **msm** package in R, based on the above-described likelihood with transition intensities that are constant in time within each group. The state occupation probabilities that are to be estimated in this sensitivity analysis can only be expected to be in agreement with the cumulative incidences that are to be estimated in the main analysis, if responders remain in the Responder state (without permanently discontinuing IMP independently of pandemic restrictions).

Proportional transition intensity regression models will also be fit, assuming the baseline transition intensities are piecewise constant in time. In other words, for a given partition of the time interval $[0, 28]$, $0 = \tau_0 < \tau_1 < \dots < \tau_P = 28$, the transition intensities will be assumed to have the form,

$$q_{jk}(t | \mathbf{x}) = q_{jkp} \exp(\boldsymbol{\beta}_{jk} \cdot \mathbf{x}) \text{ for } p \in \{1, \dots, P\}, \tau_{p-1} \leq t < \tau_p \text{ and states } j, k,$$

where $\boldsymbol{\beta}_{jk}$ is a vector of transition $j \rightarrow k$ specific regression parameters describing the treatment group, baseline body weight (≤ 100 kg, > 100 kg), and baseline PASI score. Models based on the following partitions of the time interval $[0, 28]$ will be fit:

- Constant baseline transition intensities
- Piecewise constant baseline transition intensities based on the partition of the time interval $[0, 28]$ with cut-point $\tau_1 = 14$.

For the latter partition and a given transition denoted by $j \rightarrow k$, if there are no observed transitions within a given time interval defined by the partition, the cut-points for modeling that specific transition will be reduced to ensure that at least one transition is observed within each defined time interval.

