To quantify the magnitude of the potential treatment effect, the estimated cumulative incidence functions for the competing risks model displayed in [Panel 24](#) will be presented for the groups defined by treatment arm and randomisation strata, based on the Aalen-Johansen estimator, along with 95% confidence bands. Additionally, the estimated sub-distributional hazard ratios comparing treatment arms and corresponding 95% CIs for the 2 competing risks based on fitting Fine and Gray models, stratified by baseline body weight (≤ 100 kg, > 100 kg) and adjusted for prior TNF- α inhibitor use at baseline (≤ 1 , > 1) and the baseline PASI score will be presented.

It is important to note that for endpoints that are only assessed at trial visits, e.g. PASI score, the above specified analysis implicitly ignores the intermittent inspection process. The time to achieving the endpoint, e.g. PASI 100 response, is imputed based on the trial visit where the response is first observed.

[figure not shown]
Sensitivity analysis assessing the robustness with respect to the intermittent follow-up

For a given subject in the main analysis, the time to response while remaining on treatment – interpreting permanent discontinuation of IMP due to pandemic restrictions as right censoring – is imputed using the scheduled timing of the visit where the desired response is first observed. In order to assess the robustness of the results of the primary analysis with respect to this imputation strategy, the probability of achieving a response prior to discontinuation of IMP independent of pandemic restrictions will be estimated based on the MSM illustrated in [Panel 25](#). For this analysis, the intermittent nature of the follow-up will be taken into account by formulating the individual contributions to the likelihood with respect to the transition probability matrix, as in Kalbfleisch and Lawless, 1985 ([46](#)). The estimated state occupation probabilities and expected duration of time spent in the response state will also be estimated.

THIS DOCUMENT CONTAINS CONFIDENTIAL INFORMATION AND MUST NOT BE COPIED OR MADE AVAILABLE TO ANY THIRD PARTY WITHOUT THE PRIOR WRITTEN CONSENT OF THE LEO PHARMA GROUP

Panel 25: Multi-state model for the sensitivity analysis accounting for the intermittent nature of the observation process

Abbreviations: IMP = investigational medicinal product.

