5.3 Intercurrent events

An intercurrent event refers to a post-randomisation event that either precludes the existence of or affects the interpretation of the measurements of an endpoint. For the purposes of this trial, we define the following 3 intercurrent events:

- **Permanent discontinuation of IMP independent of pandemic restrictions:** This event occurs when a subject permanently discontinues IMP for reasons not related to COVID-19 pandemic restrictions. Permanent discontinuation of IMP due to sickness with COVID-19 (an AE) will be interpreted as permanent discontinuation of IMP independent of pandemic restrictions. This event can occur either at the subject's own initiative or at the investigator's or sponsor's discretion.

Derivation of events from data: This event will be taken to have occurred if the data recorded in the 'End of treatment' eCRF form fulfil all of the following.

- 'Has the subject completed the treatment period?' is answered 'No'
- 'Primary reason for permanent discontinuation from IMP?' is not answered 'Death' or 'Lost to follow-up'
- 'Was the decision to permanently discontinue IMP related to COVID-19 pandemic restrictions?' is not answered 'Yes'.

The timing of the event will be taken as the reported 'Date of last administration of IMP'.

- **Permanent discontinuation of IMP due to pandemic restrictions:** This event occurs when a subject permanently discontinues IMP for reasons related to COVID-19 pandemic restrictions. Permanent discontinuation of IMP due to sickness with COVID-19 (an AE) will not be interpreted as permanent discontinuation of IMP due to COVID-19 pandemic restrictions. Examples of permanent discontinuation of IMP due to pandemic restrictions

THIS DOCUMENT CONTAINS CONFIDENTIAL INFORMATION AND MUST NOT BE COPIED OR MADE AVAILABLE TO ANY THIRD PARTY WITHOUT THE PRIOR WRITTEN CONSENT OF THE LEO PHARMA GROUP

are quarantines, travel limitations, subject being unable or unwilling to travel to site due to personal pandemic-related reasons, site closures, reduced availability of site staff, and interruptions to supply chain of IMP.

Derivation of events from data: This event will be taken to have occurred if the data recorded in the ‘End of treatment’ eCRF form fulfil all of the following.

- ‘Has the subject completed the treatment period?’ is answered ‘No’
- ‘Primary reason for permanent discontinuation from IMP?’ is not answered ‘Death’ or ‘Lost to follow-up’

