Notes: Subject 1 completes the treatment period, subject 2 permanently discontinues IMP independent of pandemic restrictions, subject 3 permanently discontinues IMP due to pandemic restrictions, while subject 4 becomes unblinded and subsequently permanently discontinues IMP independently of pandemic restrictions.

Depending on the estimand strategy selected, the occurrence of an intercurrent event may be ignored, lead to exclusion of data observed after the occurrence of the event, become a component in the definition of the endpoint, or restrict the relevant observation window to the time prior to the occurrence of the intercurrent event. Unblinding and permanent discontinuation of IMP – either independent of pandemic restrictions or due to pandemic restrictions – may occur to the same subject. If these intercurrent events occur on the same date, permanent discontinuation of IMP will be assumed to have occurred first. If an intercurrent event occurs on

THIS DOCUMENT CONTAINS CONFIDENTIAL INFORMATION AND MUST NOT BE COPIED OR MADE AVAILABLE TO ANY THIRD PARTY WITHOUT THE PRIOR WRITTEN CONSENT OF THE LEO PHARMA GROUP

the same date as an endpoint assessment the endpoint assessment will be assumed to have occurred first.

The number and percentage of subjects experiencing intercurrent events will be summarised by visit week interval for each treatment group.

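### The time-to-response analysis puts responses on scheduled weeks but censoring and discontinuation on calendar dates, with no rule joining the two, so the Week 28 cumulative incidence is not uniquely defined and can be biased upward

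*SAP*

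**What the plan says.** **Responses.** SAP 5.4.2.2.1, describing the main analysis, states that "the time to response while remaining on treatment is imputed using the scheduled timing of the visit where the desired response is first observed". Protocol 14.3.6.3 has the same rule: the time "is imputed using the scheduled timing of the visit where the desired response is first observed". SAP 5.4.2.1 itself says only that the time is based on the visit where response is first seen.

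**Censoring.** For both completion and withdrawal, SAP 5.4.2.1 states: "The timing of the event will be taken as the reported 'Date of last contact". SAP Section 6 reports that blind review found administrative censoring only.

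**Discontinuation.** For the competing event, SAP 5.3 states: "The timing of the event will be taken as the reported 'Date of last administration of IMP".

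**Same-date rules.** If an intercurrent event falls on "the same date as an endpoint assessment the endpoint assessment will be assumed to have occurred first" (SAP 5.3). If a censoring event falls on the date of a response or discontinuation, "the latter will be assumed to have happened first", meaning the response or discontinuation (SAP 5.4.2.1).

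**Visit window.** Protocol Section 4 allows ±3 days at every post-baseline visit, Week 28 included.

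**Multi-state sensitivity analysis.** Here a same-visit rule is explicit: response status is taken at week 20 and discontinuation is placed in its "state at the inspection time 20.1 weeks". The main analysis has no counterpart.

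**The concern.** A PASI 100 first seen at the Week 28 visit is placed at t = 28.0 whatever day the visit took place. A completer who never responded is censored on the actual day. If both are seen two days early, the responder is an event at 28.0 while the non-responder has already left the risk set at about 27.7. Leaving the risk set then depends on the outcome, although the method takes censoring as non-informative.

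The Aalen-Johansen cumulative incidence is the declared population-level summary for this estimand (Panel 5 of the protocol, Panel 2 of the SAP). SAP 5.4.2.1 presents it by arm and weight stratum, with confidence intervals for the arm differences within strata. Those outputs, and the same ones for time to PASI 90, depend on which coding the programmer picks.

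**Working it through.** **Inputs from the documents.** Protocol 14.1, scenario e)/e′), per week: brodalumab λ01 = 0.0333 and λ10 = 0.0272; guselkumab λ01 = 0.0158 and λ10 = 0.0435; 120 per arm. The 15 post-baseline visits and the ±3-day window are from protocol Section 4.

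**Assumptions.** e, the share of Week 28 visits held early, is not in the documents. A uniform spread over −3 to +3 days gives e = 3/7 = 43%. Last contact is taken as the day of the Week 28 visit. There are no competing events, as in the plan's own power model, and the test is unstratified.

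**Reproducing the plan's figures.** The model gives Week 16 response rates of 34.1% and 16.3%, and exact two-sided Fisher power of 86.9% at 120 per arm (Panel 20: 87.0%). For the key secondary endpoint, the Schoenfeld formula with hazard ratio 0.0333/0.0158 and 115.7 expected events gives 98.0%. Simulation at the scheduled visits gives 97.7% (Panel 20: 97.8%).

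**Order settled on actual dates, responses then moved to the scheduled week.** Let S26 be the share with no response seen through Week 26, and h the chance that such a subject is in response two weeks later:

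h = λ01/(λ01+λ10) × (1 − exp(−2(λ01+λ10)))

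- Brodalumab: 0.5504 × (1 − exp(−0.1210)) = 0.0627; S26 = 0.430.
- Guselkumab: 0.2664 × (1 − exp(−0.1186)) = 0.0298; S26 = 0.674.

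On one clock the last step of the curve is S26 × h. On two clocks the early non-responders, a share e(1 − h) of those left, are gone before t = 28, so the step becomes S26 × h / (1 − e(1 − h)).

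At e = 3/7:

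- Brodalumab: 0.0270/0.598 = 0.0451, an excess of 1.8 points.
- Guselkumab: 0.0201/0.584 = 0.0344, an excess of 1.4 points.

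| Early share (assumed) | Brodalumab | Guselkumab |
|---|---|---|
| 10% | +0.3 | +0.2 |
| 25% | +0.8 | +0.6 |
| 43% | +1.8 | +1.4 |
| 50% | +2.4 | +1.9 |
| 75% | +6.4 | +5.4 |

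**Simulation of each coding** (3,000 runs, uniform window, 120 per arm):

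| | One clock | Dates settle order | Literal comparison |
|---|---|---|---|
| Week 28, brodalumab | 59.6% | 61.5% | 59.9% |
| Week 28, guselkumab | 34.5% | 35.9% | 34.7% |
| Difference (points) | 25.1 | 25.6 | 25.2 |
| Power | 97.7% | 97.7% | 97.4% |
| Type I error | 5.5% | 5.6% | 5.4% |

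The Monte Carlo standard error of the type I error is about 0.4 points. Under the literal comparison an early Week 28 responder has a response time later than the last contact and is censored. That loses about one response per arm (1.05 on average).

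**Small groups.** With actual dates settling order and a uniform window, one curve is inflated by more than 5 points in about 1% of runs or fewer at 120 subjects, but in 6% to 10% at an assumed 30 subjects.

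**The case against.** The strongest reply is that this is missing detail rather than error. The SAP's Introduction sends derivation rules to the analysis data reviewer's guide and define.xml, which are not available here and may hold the mapping. Both same-date rules are written on dates, so they already settle order. The base-case shift of 1.4 to 1.8 points is confined to the last step of the curve. It is small against a binomial 95% half-width of about 8.8 points (59.5%) or 8.5 points (34.6%) at 120 per arm.

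Much of this stands. A reader might infer that one analysis suffers both inflation and lost or reordered responses. It does not: inflation needs order settled on dates, while the losses need a literal comparison of scheduled weeks with dates. A reader might also infer that the SAP prescribes sorting a response behind a discontinuation at the same visit. It does not: the SAP 5.3 rule prevents this when applied to actual dates. Even under the literal comparison it would take a first PASI 100 at an early visit with the last-ever dose that day. It cannot occur at Week 28, where no dose is given.

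What does not stand is that the same-date rules cure the problem. Applying them is what produces the inflation, because they fix order and leave the responder at 28.0 and the non-responder at an earlier date. The same Introduction also says the SAP's detail should let a reader reproduce the analyses. On this point the SAP states two explicit rules that conflict.

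**Conclusion.** The point holds as a defect in the estimated curves. With order settled on actual dates, the Week 28 cumulative incidence is biased upward whenever some Week 28 visits are early: about 1.8 and 1.4 points under a uniform window, below 1 point if a quarter or fewer are early, and above 5 points only if most are. On-time and late visits cause no inflation, so its presence in the trial's data cannot be asserted from the documents. The literal coding trades the inflation for about one lost response per arm.

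A reader might infer that the confirmatory result is at risk. The calculations do not support that: power and type I error barely move when visit timing is alike in the two arms, and the arm difference shifts by about 0.4 points against a half-width near 12.

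The sizes rest on the planning intensities, an assumed visit-timing distribution and no competing events. The number randomised is not in the documents, and the trial ended ahead of schedule (SAP Section 6), so the stratum curves may rest on few subjects.

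**What to change.** State one time scale in SAP 5.4.2.1, covering time to PASI 100 and time to PASI 90. There are two options:

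1. Settle the order of events on actual dates with the existing same-date rules. Then map responses, discontinuation and censoring to scheduled weeks, keeping that order within a week and censoring completers at Week 28.0. This fits the response rule already in both documents.
2. Use actual dates for all events. The scheduled-timing statements in SAP 5.4.2.2.1 and protocol 14.3.6.3 would then need a matching entry in SAP Section 6. The SAP should also say at which day the final value is read, since late Week 28 visits fall after day 196.

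Either takes a sentence or two before unblinding. It needs no new data and does not affect the testing hierarchy or alpha.
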